Participants who meet initial eligibility requirements at the Screening Visit (Visit 1) will be trained on the use of the eDiary and instructed on recording their qualifying prodrome events and their headache (if it occurs), nonheadache symptoms as well as all the assessments to complete on the device. In addition, the site will review the timing of the reminders and assessments as well as qualifications for a prodrome event that requires recording on the eDiary. Refer to Section 6.3.1 for the definition of a qualifying prodrome event to be recorded in the eDiary.

Participants can use rescue medication during the screening period as outlined in Section 6.5.3. Once site staff are confident that the participant understands their responsibility, a patient-specific eDiary with the participant's own prodrome symptoms preprogrammed can be dispensed to the participant. The site will instruct the participant to return with the eDiary to each future visit as the same device will be used for the duration of study participation.

During Screening Period (between Visit 1 and Visit 2)

During the screening period (between Visit 1 and Visit 2), participants will have 60 days to demonstrate the reliability of developing a headache after experiencing a qualifying prodrome event. Participants will be instructed to record their qualifying prodrome events and headaches in the eDiary. Participants who record less than 3 qualifying prodrome events in the screening period (60 days) (ie, 1 or 2 events) will be screen failed (for failure to meet inclusion criterion 2.06).

Phone Call

A phone call will be made 30 days (\pm 7 days) after Visit 1 to check in with the participants to ensure there are no issues with their eDiary and recording of the participants' responses. Review the data collected in the eDiary including compliance in answering all questions. A review of concomitant medications and review and assessment of AEs will also be conducted.

Randomization Visit (Visit 2)

Review eDiary data collected during the screening period (between Visit 1 and Visit 2) to confirm that inclusion criteria 2.06 and 2.07 (Section 5.1) are met.

Confirm that the participant has met the following criteria to be randomized:

- 3 to 16 qualifying prodrome events have been recorded during the screening period
 - For participants who record only 3 qualifying prodrome events, all events (100%) must be followed by a headache within 1 to 6 hours.

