9.4.1.4. Other Efficacy Analyses

The absence of a headache of any intensity by each timepoint after taking double-blind study intervention will be analyzed using the same GLMM model as primary endpoint. Similar analyses will be performed for the absence of a headache of moderate/severe intensity and absence of severe headache by timepoint. Kaplan-Meier curves for time to development of any intensity headache (or rescue medication taken), time to development of moderate/severe headache, time to development of severe headache within 48 hours will be produced by treatment and compared between treatment using the log-rank test. Additional Kaplan-Meier curves will be generated treating rescue medication as an event for the time to development of moderate/severe intensity headache and time to development of severe headache.

For each of the 5 most common individual prodrome symptoms, the absence of any intensity, absence of moderate/severe intensity, absence of severe intensity at each timepoint will be analyzed using the same GLMM model as primary endpoint. Similar analyses will be performed for the absence of any intensity nonheadache migraine symptom, absence of moderate/severe nonheadache migraine symptom, absence of severe nonheadache migraine symptom at each timepoint, and absence of aura at each timepoint. Kaplan-Meier curves for time to absence of prodrome symptoms will be produced by treatment and compared between treatment using the log-rank test. Kaplan-Meier curves will also be generated censoring data collected after rescue medication.

The observed proportions of participants who used rescue medication within 24 and 48 hours after taking double-blind study intervention will be summarized and analyzed using the same GLMM model as primary endpoint. The treatment comparisons will be conducted using the primary model. Kaplan-Meier curves for time to rescue medication use within 48 hours after taking double-blind study intervention will also be produced by treatment and compared by log-rank test.

Analysis methods for the endpoints of satisfaction with study medication and Activity Limitation will be specified in the SAP.

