### 3.3 Other Efficacy Endpoints

Additional efficacy endpoints along with their respective clinical objectives are listed below in bullets in respect of the purposes.

To evaluate the effect of a single dose of ubrogепant (100 mg) versus placebo, administered during the prodrome, on attenuation of the headache phase:

- Absence of headache of any intensity by timepoint (1, 2, 3, 4, 6, 8, 48 hours postdose)
- Absence of moderate/severe headache by timepoint (1, 2, 3, 4, 6, 8 hours postdose)
- Absence of severe headache by timepoint (1, 2, 3, 4, 6, 8, 24, 48 hours postdose)
- Time to development of headache of any intensity within 48 hours after taking double-blind study intervention during the prodrome (Kaplan-Meier analysis)
- Time to development of headache of moderate/severe intensity within 48 hours after taking double-blind study intervention during the prodrome (Kaplan-Meier analysis)
- Time to development of headache of severe intensity within 48 hours after taking double-blind study intervention during the prodrome (Kaplan-Meier analysis)

To evaluate the effect of a single dose of ubrogепant (100 mg) versus placebo, administered during the prodrome, on prodrome symptoms, nonheadache migraine symptoms (photophobia, phonophobia, nausea, and dizziness), and aura:

- For each of the 5 most common individual prodrome symptoms:
  - Absence of any intensity at each timepoint
  - Absence of moderate/severe intensity at each timepoint
  - Absence of severe intensity at each timepoint
  - Time to absence of any intensity
- After a headache of any intensity is reported:

- Absence of nonheadache migraine symptoms (photophobia, phonophobia, nausea, dizziness) at each timepoint
- Absence of nonheadache migraine symptoms (photophobia, phonophobia, nausea, dizziness) of moderate/severe intensity at each timepoint
- Absence of nonheadache migraine symptoms (photophobia, phonophobia, nausea, dizziness) of severe at each timepoint
- Absence of aura at each timepoint

To evaluate the effect of a single dose of ubrogепant (100 mg) versus placebo on use of rescue medication:

- Rescue medication use within 24 and 48 hours after taking double-blind study intervention
- Time to rescue medication use within 48 hours after taking double-blind study intervention (Kaplan-Meier analysis)

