**Table 2. Analysis Populations**

Population	Definition	Study Intervention
Intent-to-treat (ITT)	All randomized participants. Participants will be summarized according to the randomized study sequence intervention.	Randomized
Safety	All treated participants who take $\geq 1$ administration of study intervention. Participants will be summarized according to the study intervention they actually received.	Actual received
Modified Intent-to-treat (mITT)	All randomized participants with $\geq 1$ assessment of headache occurrence within 24 hours after taking double-blind study intervention for at least 1 qualifying prodrome event during the double-blind treatment period. Participants will be summarized according to the randomized study intervention.	Randomized

For efficacy analyses, data will be analyzed according to participants' randomization assignments, regardless of actual study intervention received.

For safety data analyses, data will be analyzed according to participants' actual study intervention received (rather than as randomized).

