A single-item measure assessing activity limitation based on a 24-hour recall will be administered as an additional health outcome measure. The measure will be used to evaluate activity limitation with a 5-level response ranging from "Not at all limited – I could do everything" to "Extremely limited." The measure will be administered at 24 hours after taking double-blind study intervention.

The following are general considerations for efficacy analyses:

- Efficacy analyses will be performed based on mITT population.
- Continuous variables will be summarized by number of participants with observed values (n), mean, standard deviation (SD), median, 1st and 3rd quartiles (Q1, Q3), minimum (min), and maximum (max).
- Categorical variables will be summarized by number of participants with observed values or events and percentages based on the specified population.
- The efficacy analyses will be performed using a GLMM in the observed binary response variable unless an imputation method is specified.
- The least squares mean (LSMEAN) estimates of the treatment effects for the primary and secondary endpoints alongside its 95% CI will be presented.

- All statistical hypothesis tests will be performed at the 2-sided 5% significance level.
- Efficacy analyses will be presented by treatment or study intervention randomized (placebo or ubrogepant 100 mg).

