**Figure 6. Determination of absence of moderate/severe headache by T hours (1, 2, 3, 4, 6, 8 hours) (responder)**

**Figure 7. Determination of absence of severe headache by T hours (1, 2, 3, 4, 6, 8, 24, 48 hrs) (responder)**

The absence of a headache of any intensity by each timepoint after taking double-blind study intervention will be analyzed using the same GLMM model as primary endpoint.

Similar analyses will be performed for the absence of a headache of moderate/severe intensity and absence of severe headache by timepoint. Kaplan-Meier curves for time to development of any intensity headache (or rescue medication taken), time to development of moderate/severe headache, time to development of severe headache within 48 hours will be produced by treatment and compared between treatment using the log-rank test. In addition, Kaplan-Meier curves for time to development of moderate/severe headache (or rescue medication taken) and time to development of severe headache within 48 hours (or rescue medication taken) will be produced. Hazard ratio will be estimated from cox proportional hazard model with treatment and period factors.

For each of the 5 most common individual prodrome symptoms, the absence of any intensity, absence of moderate/severe intensity, absence of severe intensity at each timepoint will be analyzed using GLMM with additional predose baseline prodrome symptom intensity category. In addition, prodrome symptoms will be summarized by descending frequency in ubrogепant group and by intensity at predose. Same GLMM model as the primary endpoint will be performed for the absence of any intensity, absence of moderate/severe intensity, absence of severe intensity nonheadache migraine symptom at each timepoint after a headache of any intensity is reported. The absence of aura at timepoint will be analyzed using GLMM model with additional predose baseline aura status. Kaplan-Meier curves for time to absence of each of the 5 most common individual prodrome symptoms will be produced by treatment and compared between treatment using the log-rank test. Kaplan-Meier curves will also be generated censoring data collected after rescue medication for migraine associated symptoms. Hazard ratio will be estimated from cox proportional hazard model with treatment and period factors.

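### SAP 8.5 does not limit time to absence of a prodrome symptom to events with that symptom at predose, so events without it may count as absent at 1 h and dilute the comparison

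*SAP*

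**What the plan says.** SAP 3.3 gives the endpoint, for each of the 5 most common prodrome symptoms, as "Time to absence of any intensity". SAP 8.5 gives the method: "Kaplan-Meier curves for time to absence of each of the 5 most common individual prodrome symptoms will be produced by treatment", compared by log-rank test, and "Hazard ratio will be estimated from cox proportional hazard model with treatment and period factors". Protocol 9.4.1.4 has the same curves and test and adds no condition: "Kaplan-Meier curves for time to absence of prodrome symptoms will be produced by treatment".

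The analysis set is fixed in SAP 8.1: "Efficacy analyses will be performed based on mITT population". Entry to mITT (SAP Table 2) requires at least one "assessment of headache occurrence within 24 hours after taking double-blind study intervention for at least 1 qualifying prodrome event". It says nothing about prodrome symptoms.

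For the binary analysis of the same symptoms at each timepoint, SAP 8.5 does control for the predose state. Those endpoints "will be analyzed using GLMM with additional predose baseline prodrome symptom intensity category". The version history (SAP 13.0, version 3) explains that the predose effect should be controlled in the model.

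On data collection, Protocol Section 8 (Screening Visit) provides a "patient-specific eDiary with the participant's own prodrome symptoms preprogrammed". Protocol 8.1 and SAP 8.1 then have each identified symptom rated absent or present up to 48 hours.

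**The concern.** Time to absence has a clear meaning only for an event in which the symptom was there to begin with. A qualifying prodrome event (Protocol 6.3.1) needs a clinically identifiable prodrome, not any particular symptom, so one of a participant's listed symptoms can be absent when the dose is taken. SAP 10.2 expects this: for the screening period it defines a prevalence rate for each symptom across qualifying events. It also restricts the symptom positive rate to events with the symptom. SAP 8.5 has no matching restriction, and no statement of the at-risk set or of how an event without the symptom is handled.

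If such an event is programmed as it stands, its first record of absence is the 1 h assessment. It then counts as an early success in either arm. What is at stake is whether the curves, log-rank test and hazard ratio for each symptom describe resolution of that symptom, or partly describe how often it was missing.

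**Working it through.** The documents give no power, prevalence, hazard ratio or median for these endpoints, so there is no plan figure to reproduce. The size has to be shown over a range.

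**Inputs from the documents.** Assessments at 1, 2, 3, 4, 6, 8, 24 and 48 h (Protocol 4.1). Two-sided 5% level (SAP 8.1). Effective sample size of 480 participants (SAP 2.4).

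**Assumptions.** 480 events per arm, which needs all 480 participants to treat both events. Exponential time to absence with placebo median 10 h and hazard ratio 1.3 among events with the symptom. Predose prevalence p from 20% to 80%. Every event without the symptom is scored absent at 1 h. Events are treated as independent.

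**Step 1: share counted absent by 1 h.** Among events with the symptom, placebo is 1 − 2^(−1/10) = 6.7% and ubrogepant is 1 − 2^(−1.3/10) = 8.6%, a mean of 7.7%. In the unrestricted set the share is (1 − p) + p × 7.7%:
- p = 80%: 20% + 6.1% = 26%
- p = 60%: 40% + 4.6% = 45%
- p = 40%: 60% + 3.1% = 63%
- p = 20%: 80% + 1.5% = 82%

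At 40% prevalence or less, the median falls at the first assessment.

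**Step 2: why the test loses power (p = 60%, expected counts).** At each time the log-rank numerator adds U = d1 − d·n1/n and the variance adds V = d(n1/n)(n0/n)(n − d)/(n − 1).
- Restricted, at 1 h: n = 576, d = 44.1, U = 2.77, V = 10.2.
- Unrestricted, at 1 h: 2 × 480 × 40% = 384 events are added to both n and d, so n = 960, d = 428.1, U = 2.77, V = 59.4.
- After 1 h the added events have left, so the two analyses have the same risk sets and contributions.

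The total numerator is 25.3 in both. The total variance rises from 78.9 to 128.1. So z = 25.3/√78.9 = 2.85 falls to 25.3/√128.1 = 2.24, and Φ(z − 1.96) goes from 81% to 61%.

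**Step 3: simulated log-rank power**, with the number of events without the symptom free to vary by arm:

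| Prevalence | Restricted | Unrestricted |
|---|---|---|
| 80% | 91% | 83% |
| 60% | 83% | 63% |
| 40% | 62% | 38% |
| 20% | 37% | 18% |

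The method of step 2 gives 91/82, 81/61, 64/39 and 37/19, within about 2 points throughout.

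**Step 4: other assumptions.** With hazard ratio 1.4 and placebo median 8 h, power is 96% vs 82% at 60% prevalence and 85% vs 57% at 40%. The Cox hazard ratio is about 1.36 vs 1.22 and 1.37 vs 1.14. Medians of 3 h and 16 h (60% prevalence) give 97% vs 90% and 95% vs 79%. With no drug effect, the unrestricted test rejects in 4.7% to 5.0% of runs. At 100% prevalence the two analyses are identical.

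**The case against.** The strongest reply is that the SAP is silent, and silence is not an instruction to count these events as successes. A reader might infer that every event without the symptom enters as an immediate success. The documents do not say so.

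- At each event the participant identifies their symptoms (Protocol 4.1, eDiary Assessments), and it is the identified symptoms that are followed. If identification means at that event, a symptom not identified has no follow-up record to be scored absent.
- A symptom that is not on the participant's preprogrammed list would probably be missing rather than absent. Only a listed symptom rated absent at predose can dilute the analysis in the way described.
- Table and figure specifications are in a separate document (SAP 1.0), which may restrict the set.

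All of this stands. It makes the figures an upper bound on the dilution under the stated assumptions. It does not close the gap, because a data-collection sentence is not an analysis-set rule and identification at the event is only one reading.

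It is also fair that the GLMM adjusts for predose intensity at every timepoint, and that SAP 8.5 summarises symptoms by predose intensity. Readers will therefore see the prevalence and a baseline-adjusted result. That limits the harm, but leaves the time-to-event results without the same control.

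**Conclusion.** The point holds as an omission with a probable direction and an unknown size. SAP 8.5 sets no presence condition and leaves predose state out of the Cox model, while controlling for it in the GLMM for the same symptoms. Where events without the symptom are counted as absent at 1 h, the curves shift early and the log-rank test and hazard ratio are diluted. On the assumptions above, the loss of power is at most about 8 points at 80% prevalence (91 − 83), 20 at 60%, 24 at 40% and 19 at 20%. Fewer than 480 events per arm would lower both columns, and SAP 2.4 says only that some participants will contribute two events.

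Two stronger readings are not supported. The documents give no prevalence, so one cannot say that the median mostly reflects how rare a symptom is, least of all for the five most common. Nor is there a risk of false positives: type I error stays near 5%, and any dilution works against finding an effect. These are additional endpoints outside the sequence in SAP 12.0, so the primary and secondary conclusions and the sample size are unaffected.

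**What to change.** In SAP 8.5, restrict each symptom's Kaplan-Meier, log-rank and Cox analyses to treated events with that symptom present (mild or worse) at predose. Add predose intensity category to the Cox model, as version 3 already does for the GLMM. State the time origin, the event and the censoring rule in the same place. If the figure specifications already restrict the set, the added text only records it.

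The cost is one or two sentences and no new data. Fewer events remain per symptom, but under this scoring those removed carry no information on resolution. One caveat belongs with the change: predose status in period 2 follows period 1 treatment, so the restriction is not wholly free of dependence on treatment. The minimum 7-day washout should keep this small.

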## **8.6 Efficacy Subgroup Analyses**

Subgroup analyses of the primary efficacy endpoint will be performed by current exposure (yes/no) to a migraine prevention medication with proven efficacy, and by allodynia status by history (absence/presence).

Additional subgroup categories that may be considered are:

- Exposure to a migraine prevention medication (current, past and none)
- Triptan therapy historical response (triptan responders, triptan naïve, and triptan non-responder)
- Optimization of triptan therapy historical response (triptan responder, triptan optimized, triptan unoptimized)
- Cardiovascular disease (presence or not)
- Cardiovascular risk (presence or not)
- Cardiovascular risk (none, only 1 risk factor, 2 and more risk factors)
- Failed prevention medication (yes or no)

## **9.0 Safety Analyses**

### **9.1 General Considerations**

- Safety analyses will be performed based on the safety population.
- Safety analysis will be presented by treatment or study intervention participants actually received (placebo or ubrogepant 100 mg) unless specified otherwise.
- The baseline for safety endpoints is defined as the last non-missing assessment prior to the first dose of the double-blind study intervention.

## **9.2 Adverse Events**

### **9.2.1 Treatment-Emergent Adverse Events**

An AE will be considered a treatment emergent adverse event (TEAE) if the AE began or worsened (increased in severity or became serious) on or after the date (and time, if known) of the study intervention. However, AEs that occurs more than 30 days after the Period 1 study intervention and before the date of the Period 2 study intervention and AEs that occurs more than 30 days after Period 2 study intervention will not be counted as a TEAE. A TEAE will be assigned to a study intervention if it occurred on or after the date of the study intervention and before the date of the next study intervention. An AE will be assigned to the last study intervention of the treatment sequence if it occurred on or after the date of the last study intervention. An AE will be considered a treatment-emergent serious AE (TESAE) if it is a TEAE that additionally meets any SAE criterion.

AEs will be coded using the Medical Dictionary for Regulatory Activities (MedDRA) version 23.1 or higher.

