9.4.2.1. Adverse Events

An AE will be assigned to a study intervention if it occurred on or after the first dose of the study intervention and before the first dose of the next study intervention. An AE will be assigned to

the last study intervention of the treatment sequence if it occurred on or after the first dose of the last study intervention.

AEs will primarily be assessed through the analysis of AEs reported in the 48 hours following the administration of study intervention. A supportive analysis will include AEs reported within 30 days after the last dose of the study intervention (and before the first dose of the next intervention if any).

An AE will be considered a TEAE if the AE began or worsened (increased in severity or became serious) on or after the date (and time, if known) of the first dose of study intervention. However, an AE that occurs more than 30 days after the Period 1 study intervention and before the date of the Period 2 study intervention and an AE that occurs more than 30 days after the Period 2 study intervention will not be counted as a TEAE.

An AE will be considered a TESAE if it is a TEAE that additionally meets any SAE criterion.

The number and percentage of participants with TEAEs in each study intervention will be tabulated by system organ class and preferred term and by system organ class, preferred term, and severity.

The number and percentage of participants with treatment-related TEAEs in each study intervention will be tabulated by system organ class and preferred term.

If more than 1 AE is coded to the same preferred term for the same participant on the same study treatment, the participant will be counted only once for that preferred term using the most severe and most related occurrence for the summarizations by severity and by relationship to study intervention.

Summary tables will be provided for participants with TESAEs and participants with TEAEs leading to discontinuation. Listings of all AEs, SAEs, and AEs leading to discontinuation by participant will be presented.

The definitions of an AE and SAE can be found in Section 10.3 (Appendix 3).

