### **9.2.3 Treatment-Emergent Adverse Events by SOC and/or PT**

AEs will primarily be assessed through the analysis of AEs reported in the 48 hours following the administration of each study intervention. A supportive analysis will include AEs reported within 30 days after the study intervention (and before the next intervention if any). Unique participants reporting AEs will be summarized in the following AE categories by treatment and total for the safety population in double-blind treatment period.

- TEAEs by SOC and PT.
- TEAEs by SOC, PT and severity. If more than 1 AE is coded to the same PT for the same participant, the participant will be counted only once for that PT using the maximum severity for the summarization by severity. If the severity of a TEAE is missing, the maximum severity will be assigned to the event for the summarization by severity. The value will be displayed as missing in the data listing.
- Treatment-related TEAEs by SOC and PT. If more than 1 AE is coded to the same PT for the same participant, the participant will be counted only once for that PT using the closest causal relationship to treatment for the summarization by causal relationship. If the relationship to the study intervention is missing for a TEAE, the event will be considered related to the study intervention for the summarization. The value will be displayed as missing in the data listing.
- The incidence of common ( $\geq 2\%$  [after rounding] of participants in either study intervention) TEAEs will be summarized by descending frequency in the ubrogepant group.

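### SAP 9.2.1 assigns TEAEs to a treatment by calendar date rather than by dose, so an AE that starts before the second dose on that day is charged to a drug not yet taken

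*SAP*

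**What the plan says.** **Attribution.** Protocol 9.4.2.1 assigns an AE to an intervention if it occurred "on or after the first dose of the study intervention and before the first dose of the next study intervention". SAP 9.2.1 assigns a TEAE if "it occurred on or after the date of the study intervention and before the date of the next study intervention", and gives an AE to the last intervention of the sequence "if it occurred on or after the date of the last study intervention". Both SAP sentences refer to the date; the protocol refers to the dose.

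**Treatment-emergence.** Here the SAP does use the clock. An AE is a TEAE if it began or worsened "on or after the date (and time, if known) of the study intervention". The protocol has the same device: "on or after the date (and time, if known) of the first dose of study intervention".

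**Windows.** SAP 9.2.3 makes the first 48 hours after each dose the primary AE analysis. Its supportive analysis runs to 30 days and stops at the next intervention, not at the next intervention's date. The 30-day exclusion in SAP 9.2.1 is bounded by the date of the Period 2 intervention, and Protocol 9.4.2.1 words that exclusion the same way.

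**Repeated preferred terms.** The protocol's rule begins "If more than 1 AE is coded to the same preferred term for the same participant on the same study treatment". The severity bullet in SAP 9.2.3 says that, when a term recurs "for the same participant, the participant will be counted only once for that PT using the maximum severity", and the relatedness bullet has the same form. Neither bullet carries the protocol's per-treatment qualifier.

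SAP Appendix F, which lists changes from the protocol's planned analyses, mentions neither wording difference.

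**The concern.** In a two-period crossover, the attribution rule decides which column an AE appears in. A date rule and a dose rule differ only in the hours before dosing on the second dosing day. An AE that starts in those hours can only have followed the first treatment, yet the SAP charges it to the second.

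The SAP also disagrees with itself. Section 9.2.1 uses a known onset time to decide that the AE is treatment-emergent, then ignores that time when choosing the treatment. In the 30-day analysis, 9.2.3 puts the same AE in the first treatment's window while 9.2.1 labels it with the second. If a programmer applies both rules together, the AE fits neither column. The SAP does not say which rule governs.

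At stake are individual by-treatment entries. For a common mild event this is negligible. For a rare serious event, or one leading to discontinuation, a single wrong label is visible.

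**Working it through.** The plan states no figure on this point, so there is none to reproduce. The check applies both rules to test onsets, then sizes the affected window.

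**1. Both rules on test onsets.** Assumed clock times: dose 1 on day 1 at 09:00, dose 2 on day 8 at 13:00 (the minimum separation of 7 days is in Protocol 4.1).

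| Onset | Hours after dose 1 | Dose rule | SAP date rule | In a 48-hour window? |
|---|---|---|---|---|
| Day 1, 07:00 | −2 | not a TEAE | not a TEAE | no |
| Day 1, 10:00 | 1 | Period 1 | Period 1 | yes, dose 1 |
| Day 3, 08:00 | 47 | Period 1 | Period 1 | yes, dose 1 |
| Day 8, 08:00 | 167 | **Period 1** | **Period 2** | no |
| Day 8, 14:00 | 173 | Period 2 | Period 2 | yes, dose 2 |

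Only the pre-dose onset on day 8 changes. There is no matching error on the first dosing day, because an AE with a known time before dose 1 is not a TEAE.

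**2. Reach into the primary analysis.** The earliest affected onset is midnight at the start of the second dosing day. With doses at least 7 days apart, that is at least 7 × 24 − 24 = 144 hours after dose 1, well beyond 48 hours. It also precedes dose 2, so it is in neither 48-hour window.

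**3. The 30-day exclusion.** Assume dose 1 on day 1 at 09:00, dose 2 on day 36 at 13:00 (the treatment period allows up to 60 days), and onset on day 36 at 08:00. Onset is 35 × 24 − 1 = 839 hours after dose 1, beyond 30 × 24 = 720. It is not before the date of the Period 2 intervention, so it is not excluded, and SAP 9.2.1 gives it to the second treatment. With the cut at the dose, it would be excluded.

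**4. Share of the Period 1 window affected.** Formula: pre-dose hours / (gap in days × 24). Dosing is assumed between 06:00 and 14:00, consistent with the recommendation in Protocol 6.3.1 to treat morning or early-afternoon events.

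- 7-day gap: 6/168 = 3.6% to 14/168 = 8.3%
- 14-day gap: 6/336 = 1.8% to 14/336 = 4.2%
- 30-day gap: 6/720 = 0.8% to 14/720 = 1.9%

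These are shares of time, not of AEs.

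**5. Share of participants.** Formula: weekly AE onset rate × pre-dose hours / 168. Assumed: 3% to 10% of participants with an onset per week, and 4 to 10 pre-dose hours; neither is in the documents.

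- Low: 0.03 × 4 / 168 = 0.07%
- High: 0.10 × 10 / 168 = 0.60%

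If all 516 randomized participants treated a second event, that is 516 × 0.0007 = 0.4 to 516 × 0.0060 = 3.1 participants. Taking the full 14 hours from step 4 raises the upper end to 0.10 × 14 / 168 = 0.83%, or 4.3 participants.

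**6. Direction.** In Sequence A (placebo, then ubrogepant) a misassigned AE moves from placebo to ubrogepant. In Sequence B it moves from ubrogepant to placebo. Randomization is 1:1.

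**7. Repeated terms.** The sentence introducing the SAP 9.2.3 bullets has unique participants summarized for each treatment and in total. Built that way, a participant with the same term in both periods counts once in each treatment column and once in the total. Restoring the protocol's qualifier changes no by-treatment count.

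**The case against.** The strongest reply is that this is wording with almost no consequence. Much of it stands.

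- The primary 48-hour analysis is untouched when onset time is known (step 2). When the time is missing, any workable rule falls back on the date, so the proposed change alters nothing there.
- The protocol's attribution sentence says dose and does not mention clock time. Explicit time wording occurs only in the TEAE definition, which the SAP keeps. The protocol's own 30-day exclusion is date-based, so on that item the SAP inherits the weakness.
- The shifts run in opposite directions in the two sequences, so no bias toward either treatment is shown.

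Three stronger readings are tempting, and the documents do not support them.

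- A reader might infer that prodrome symptoms, which by design begin before dosing, would be charged wholesale to the second drug. Protocol 10.3.1 keeps expected symptoms of the disease under study out of AEs unless they are more severe than expected, and the side-effects diary covers the 48 hours after dosing.
- A reader might infer that the main AE comparison is distorted. Step 2 shows that it is not.
- A reader might infer from the repeated-term bullets that a participant with the same term on both treatments loses one entry. That needs the counting rule to run across treatment columns, against the by-treatment layout stated in the same section. SAP 7.3 uses the same shorthand for medications summarized by treatment, and the plain bullet for TEAEs by SOC and PT has no such rule.

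What the reply does not remove is that 9.2.1, followed literally, gives a wrong assignment for a definable set of AEs and contradicts both its own TEAE definition and 9.2.3.

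**Conclusion.** The point holds as a narrow defect in SAP 9.2.1. Assignment by date departs from the protocol's cut at the dose and misplaces AEs that start before the second dose on the second dosing day. Those more than 30 days after dose 1 also escape exclusion. The consequence is confined to the 30-day supportive analysis and to the overview, TESAE and discontinuation tables (SAP 9.2.2 and 9.2.4), for which no 48-hour limit is stated.

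The size is small: about 0.07% to 0.6% of participants treating a second event, or roughly 0.4 to 3 people, split between the two directions. This rests on assumed onset rates and pre-dose hours and on onsets spread evenly over time. The conclusion about the primary analysis rests on a known onset time and the 7-day minimum separation.

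The repeated-term wording is a gap to close for clarity. It is not shown to change any count.

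**What to change.** 1. **SAP 9.2.1, attribution.** Assign each TEAE to the most recent dose at or before its onset date and time; use the date alone only when the time is missing. Apply this to both attribution sentences.
2. **SAP 9.2.1, 30-day exclusion.** Bound it by the Period 2 dose in the same way, with the same fallback. Because the protocol's exclusion has the same date wording, record the change in Appendix F.
3. **SAP 9.2.3.** State that the 30-day window uses the 9.2.1 cut, so that the two sections cannot give different answers.
4. **SAP 9.2.3, clarification only.** Restore the protocol's per-treatment qualifier in the severity and relatedness bullets, with one count per participant in the total column.

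The cost is a few phrases and no new data collection. Dose date and time are already in the eDiary (Protocol 6.4), and the side-effects diary records date and time for effects after dosing. For other AEs the rule uses onset time where it was recorded, as the TEAE definition already does.
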